6.3.3 Exploratory Secondary Safety and Efficacy Analyses

The exploratory secondary safety and efficacy endpoints listed in section 6.2 will be analyzed as described in **Table 7** (next page). In brief, all study data will first be summarized using standard descriptive statistics as appropriate based on data type and distribution. Assessments of change over time for all longitudinal secondary outcome data will first be assessed graphically, with and without stratification by the administered tobramycin dose. Next, paired t-tests or Wilcoxon sign rank tests will be used to compare

pre-trial baseline values to those recorded at later time points. Non-paired tests will be used to compare data baseline and subsequent data points between the infants in the phase 1 trial and observational (non-treated) cohorts.

	Values available for:			
Study outcome	Phase 1 trial cohort	Observational cohort	Statistical approach	
Secondary safety endpoints	Yes	Yes, for some endpoints	 Rates of the secondary tolerability endpoints will be summarized for each dose level. Descriptive, narrative details of these endpoints will also be provided as appropriate. Data on the rates of endotracheal tube obstruction, unplanned tracheal extubation, and audiology testing results will be compared between the trial and observational cohorts. Planned comparisons of audiology testing results are described in the Protection of Human Subjects document. 	
Secondary efficacy endpoints				
Negative TA culture for the target GNR	Yes	No	 Primary exploratory efficacy endpoint. Rates will be summarized for the trial cohort as a whole and stratified by drug dose level. 	
Change in TA GNR pathogen CFU	Yes	No	 Absolute (pre vs post) and relative change ([post trial – pre trial] / pre trial) in the target organism CFU/mL on the log₁₀ scale will be calculated for each phase 1 trial participant. Paired t-tests or Wilcoxon sign rank tests as appropriate will be used to compare pre- vs. post-trial absolute CFU/mL values for the whole cohort and stratified by drug dose level. 	
Tracheal aspirate tobramycin levels	Yes	No	 Values, stratified by drug dose, will be compared to established concentrations necessary to overcome the minimum inhibitory concentration needed to kill 90% of detected bacterial isolates (MIC₉₀).^{90,91} Values will also be used in our PK analyses. 	

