Tracheal aspirate cytokine levels	Yes	No	 Individual cytokine levels measured pre-trial, ≤48 hours after the final dose, and 14 days after the final drug dose will be summarized. Transformation (e.g. logarithmic) or categorization by centiles will be considered based on the data distribution. Correction for total protein levels in the tracheal aspirate will be employed to account for differences in dilution during sample collection. The relative intra-patient change for the individual cytokine levels 	
			 from pre-trial baseline to the 2 post-trial timepoints will be calculated and compared between dose levels. The association between change in cytokine levels and tobramycin dose will be explored using bivariate and multivariate correlation analyses with Bonferroni correction for multiple testing.¹⁰⁰ We will consider exploratory cluster and linear discriminate analyses to identify airway immunological profiles associated with differences in the response to inhaled tobramycin (e.g. change in CFU/mL).^{101,102} 	
Respiratory support measures Hypoxemia (SpO ₂ <80%)	Yes	Yes	 Continuously recorded FiO₂, MAP, and RSS values will be converted to time-weighted daily averages for each study day. Continuously recorded SpO₂ data will be used to calculate daily rates of intermittent and prolonged hypoxemia and daily total hypoxemia exposure. Assessment of longitudinal change using linear mixed effects models will be considered. 	
Pulmonary mechanics	Yes	Yes	 Infants in both study cohorts will undergo pulmonary mechanics measurements pre-trial, after 7d, and after 14d. Intra-patient change, relative to pre-trial baseline, will be calculated for each participant and compared (1) between the two cohorts and (2) stratified by drug dose. Assessment of longitudinal change using linear mixed effects models will be considered. 	

Table 7. Planned statistical techniques and data availability for the phase 1 trial outcomes

CFU, colony forming units; GNR, Gram-negative rod; TA, tracheal aspirate

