We will *consider* constructing exploratory linear mixed effects models to evaluate the longitudinal change in repeated measures outcome data. Owing to the modest total study sample size and low numbers of infants treated with each tobramycin dose, these analyses will only be performed on an exploratory basis if graphical evaluations of the study data suggest strong evidence of a linear change over the course of the study period. These models will be considered: (1) for the phase 1 trial participants as a whole, (2) with stratification by the administered dose of inhaled tobramycin, and (3) between infants who participate in the phase 1 trial and those enrolled in the observational (non-treated) cohort (for the study outcome data collected in both cohorts). Treatment dose group and treatment week will be included in the models as independent variables (the latter is added to account for natural fluctuation in disease acuity over time). Random effects for intercept +/- slope will be considered based on their effect on model fit assessed using the Akaike information criterion. Backwards, stepwise elimination techniques to determine inclusion of possible confounding, independent covariates will be employed to account for measured differences between comparison groups. Adherence to accepted numbers of independent covariates based on the study sample size will be used to avoid model over-fitting.⁹⁸ If longitudinal models are performed, 95% confidence intervals for all estimates of effect will be reported and caution will be urged when interpreting these hypothesis generating results.

Patterns in the airway microbiome will be assessed by comparing (pre vs. post treatment) measures of alpha diversity (e.g. species counts, Shannon index) and beta-diversity (Weighted and unweighted UniFrac distances⁹⁹). Principal coordinate analyses and evaluation of dominant taxa will also be used to compare the microbiome before versus after completing treatment and with stratification by the administered dose of inhaled tobramycin. Linear mixed effects models, appropriate for repeated measures data, will also be constructed to measure the association between the dose of inhaled tobramycin and measures of alpha diversity.

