6.4 Sample Size and Power

The traditional 3+3 design is the prevailing method for conducting phase 1 drug trials.^{103,104} The sample size for this design is dictated by the number of different dosages investigated in the trial and whether or not additional patients are added to individual dosage levels based on the occurrence of a toxic drug response. Up to 24 infants are expected to provide analyzable trial data as described in section 3.3.2. The purpose of the 3+3 trial design is to continue dose escalation (within set boundaries) until at least two patients among a cohort of three to six patients experience dose-limiting toxicities (i.e., \geq 33% of patients with a doselimiting toxicity at that dose level).^{103,104} If the 300mg dose level is completed in 3 participants and none show evidence of a toxic response, up to 3 additional infants will be enrolled to receive to receive 300mg. The trial will be stopped if 2 of the additional infants receiving 300mg develop a toxic response and the 216mg dose will be used as the maximum tolerated dose in subsequent trials.

Enrollment in the observational cohort will run concurrent with enrollment in the phase 1 trial. A minimum of 12 infants and a maximum of 28 infants will be enrolled in the observational cohort. This variable enrollment number is selected to avoid delay in study closure if enrollment in the trial cohort out paces the observational cohort. Importantly, these numbers are anticipated to provide adequate statistical power to measure clinically meaningful differences in the frequency of intermittent hypoxemia, an important measure of cardiorespiratory stability.^{96,97} Premature infants with BPD average 75 (SD \pm 9) intermittent hypoxemic events (SpO₂ <80% for 10s-3min) per day during the first several months of life.^{105,106} A sample size of 12 infants in the observational cohort and 12 in the trial cohort will provide >80% power (α =0.05) to detect a 15% difference in the mean daily frequency of intermittent hypoxemic events between the two groups. A sample size of 24 infants per group will provide >80% to detect an 11% difference in in the mean daily frequency of intermittent hypoxemic events.

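### Section 6.4 powers a single between-cohort test of intermittent hypoxemia that section 6.3.3 and Table 7 never define

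*Combined protocol and SAP*

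**What the plan says.** Section 6.4 attaches an alpha and a power to one comparison between the cohorts. Twelve infants in each "will provide >80% power (α =0.05) to detect a 15% difference in the mean daily frequency of intermittent hypoxemic events between the two groups". For the larger size, "A sample size of 24 infants per group will provide >80% to detect an 11% difference". The inputs are a mean of 75 events per day and an SD of 9. The same section sets the observational cohort at 12 to 28 infants and describes those numbers as adequate for this outcome.

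Section 6.3.3 describes the analysis. Pre-to-later comparisons within infants get named tests (paired t or Wilcoxon signed rank). The between-cohort comparison gets only this: "Non-paired tests will be used to compare data baseline and subsequent data points between the infants in the phase 1 trial" and the observational cohort. The hypoxemia row of Table 7 adds a data reduction, "Continuously recorded SpO₂ data will be used to calculate daily rates of intermittent and prolonged hypoxemia and daily total hypoxemia exposure", and says that mixed models will be considered. Of those models the text says that "these analyses will only be performed on an exploratory basis if graphical evaluations of the study data suggest strong evidence of a linear change". A multiplicity correction (Bonferroni) is stated only for the cytokine correlations.

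Sections 5.3 and 6.2 define the hypoxemia endpoint as a change. It is labelled exploratory throughout.

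**The concern.** Power and alpha belong to a specific test of a specific quantity. Section 6.4 implies one test of one number per infant. An analyst who follows section 6.3.3 never reaches that test: there is no 14-day summary, no decisive day, no named test and no order of precedence. The only analysis that pools days depends on how the plots look.

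Several different results could then be presented as the powered comparison: a single day, the last day, a period mean, a change from baseline, or a model slope. A difference that is significant on day 9 but not on day 13 could be reported either way. This matters because the comparison is the only one with a stated alpha and power, and section 9.4.3 says the data will inform phase 2 and 3 designs.

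**Working it through.** **1. Reproduce the stated power.** Inputs from section 6.4: mean 75, SD 9, alpha 0.05. Sidedness is not stated; two-sided is assumed. For a two-sample t-test with n per group, the noncentrality is difference / (SD × √(2/n)), on 2n − 2 degrees of freedom.

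| n per group | Difference | Noncentrality | Power, two-sided t |
|---|---|---|---|
| 12 | 0.15 × 75 = 11.25 | 11.25 / (9 × √(2/12)) = 3.06 | 83.3% |
| 24 | 0.11 × 75 = 8.25 | 8.25 / (9 × √(2/24)) = 3.18 | 87.5% |

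Both agree with the claim of more than 80%. They do so as one test at the full 0.05, with no allowance for repeated testing. The 12 v 12 figure stays above 80% only while the SD is at most about 9.4.

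**2. Look for that test in the analysis section.**
- Section 6.3.3, between cohorts: unnamed non-paired tests at baseline and later data points.
- Table 7, hypoxemia row: one rate per day; mixed model optional.
- Section 6.3.3, mixed model: only if the plots suggest a linear change.
- Multiplicity rule for hypoxemia: none.

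None of these is a single comparison of mean daily frequency.

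**3. What day-by-day testing could cost.** Assumption: each of the 14 study days is tested at 0.05. If days were independent, the chance of at least one false positive is 1 − 0.95^14 = 51.2%. Days within an infant will be correlated, and the documents give no correlation, so a range was simulated: 20,000 null trials per setting, 12 v 12, normal daily values, two-sample t-test each day.

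| Correlation parameter | Exchangeable | Decaying by day, AR(1) |
|---|---|---|
| 0.2 | 47% | 50% |
| 0.5 | 35% | 47% |
| 0.7 | 26% | 40% |
| 0.9 | 15% | 25% |
| 0.95 | 11% | 18% |

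**4. Compare the remedies.** One pre-specified test keeps the false-positive rate at 5% and the power in step 1. Bonferroni over 14 days would use 0.05/14 = 0.0036 per day. Per-day power would then be 44% (12 v 12) and 55% (24 v 24), if SD 9 applies to a single day's count.

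**The case against.** The strongest reply is that the endpoint is exploratory. Escalation, stopping and the maximum tolerated dose rest on the toxicity endpoint and the 3+3 rule alone. Section 6.4 says the observational cohort's variable size was chosen to avoid delaying closure; the power statement only supports that range. This stands: no confirmatory error rate exists to be lost. It does not remove the gap, because the plan still makes a claim with an alpha, a power and an effect size for an analysis it does not define. The caution section 6.3.3 urges about interpretation is attached to the longitudinal models, not to the non-paired tests.

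The second reply is that the plan never says every day is tested. This also stands. The sentence is a brief summary covering all longitudinal outcomes, including mechanics measured three times, and the mixed models use treatment week as their time unit. A reader might infer that the plan carries a family-wise false-positive rate of about one in three. The documents do not support that as a fact: they give no number of tests, no per-test alpha for the daily values and no between-day correlation.

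The third reply concerns the remedy. A plain post-baseline mean would ignore the baseline although the endpoint is a change, and families choose the cohort, so an alpha-controlled test does not make the groups comparable. Both points are right. The contrast should use the day 0 value and keep its exploratory label.

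**Conclusion.** The concern holds as a mismatch between sections 6.4 and 6.3.3. The power arithmetic is sound on its own inputs, but it describes a test that the analysis section does not contain. The consequence is room to choose the reported result after seeing the data.

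The false-positive figures illustrate the possible size of that room. They rest on 14 daily tests at 0.05 and an assumed correlation. Under that daily-testing assumption, even the most favourable correlation examined (exchangeable, 0.95) gives about twice the 0.05 quoted in section 6.4. The finding does not depend on any one of these values.

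It would go too far to conclude that the trial's error control fails or that its dose decisions are affected. This comparison feeds no such decision.

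**What to change.** In section 6.3.3 and the hypoxemia row of Table 7, name one between-cohort contrast for intermittent hypoxemia:

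- **Summary:** each infant's mean daily event rate over the available study days 1-14. Using available days gives a value for infants who leave early.
- **Test:** one comparison between cohorts at two-sided 0.05, adjusted for the infant's day 0 rate and run whatever the plots show. Adjustment also brings the analysis closer to the change endpoint in section 6.2.
- **Daily values:** plots with intervals and no p-values.
- **Section 6.4:** state that the power refers to this contrast, quoting 83% (12 v 12, 15% difference) and 87% (24 v 24, 11% difference) as the unadjusted figures.
- **Status:** say that the contrast remains exploratory because the cohorts are not randomised.

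Table 1 schedules day 0 oximetry for both cohorts. The text on the observational cohort (section 3.1.3) mentions only the 14-day period, so it should be aligned with Table 1.

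The cost is a few sentences, no data beyond what Table 1 already schedules, and fewer tests. The small downside is that an effect confined to a few days would be described but not tested.

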Statistical and Analytic Plan	All subjects entered into the phase 1 trial will be included in the primary safety analysis. The primary study outcome, listed above under "Safety Evaluations," will be evaluated as a dichotomous outcome based on the presence of any of the listed outcomes. A 3+3 design will be followed to determine enrollment and trial progression based on the results of each infant's safety analysis.
DATA AND SAFETY MONITORING PLAN	A 4-member independent data safety monitoring board (DSMB) consisting of 2 neonatologists, 1 statistician, and 1 audiologist will monitor trial data, safety, progress throughout the trial.

TABLE 1: SCHEDULE OF STUDY PROCEDURES	;
---------------------------------------	---

Study Phase	Screening	Phase 1 Trial														Follow-up		
Study Days		0 ^a	1	2	3	4	5	6	7	8	9	10	11	12	13	14	15 ^b	>15
Informed consent	Х																	
Review inclusion & exclusion criteria	Х																	
Pre-trial medical record review	Х																	
Prior & concomitant medications	Х																	
Dispense study drug			Х	Х	Х	Х	Х	Х	Х	Х	Х	Х	Х	Х	Х	Х		
Review current medications		Х	Х	Х	Х	Х	Х	Х	Х	Х	Х	Х	Х	Х	Х	Х	Х	
Review all laboratory, imaging data		Х	Х	Х	Х	Х	Х	Х	Х	Х	Х	Х	Х	Х	Х	Х	Х	
Continuous pulse oximetry		Х	Х	Х	Х	Х	Х	Х	Х	Х	Х	Х	Х	Х	Х	Х		
Pulmonary mechanics measurements		Х							х								х	
Tracheal aspirate	Х	Х				Х			5X			Х				Х	2X	2X ^c
Blood draw for laboratory testing - Serum tobramycin trough - Comprehensive metabolic panel ^d			х			x			x			x				x		
Blood peak/trough for PK									2X									
Collect blood sample during clinical draws for PK analyses ^e			Х	х	Х	х	х	х	Х	х	х	х	х	х	х	х		
Assessment of respiratory support		Х	Х	Х	Х	Х	Х	Х	Х	Х	х	Х	Х	Х	Х	х	Х	
Adverse event assessment (daily)		Х	Х	Х	Х	Х	Х	Х	Х	Х	Х	Х	Х	Х	Х	Х	Х	
Adverse event assessment (weekly)																		Х
Review clinical audiology testing results	х																	х
Discharge medical record review																		Х
							Obser	vationa	l (non-t	treated)	cohort							
Tracheal aspirate	Х																Х	
Continuous pulse oximetry		Х	Х	Х	Х	Х	Х	Х	Х	Х	Х	Х	Х	Х	Х	Х		
Assessment of respiratory support		Х	Х	Х	Х	Х	Х	Х	Х	Х	Х	Х	Х	Х	Х	Х	Х	
Pulmonary mechanics measurements			х						х								х	
Review clinical audiology testing results	х																	Х
Discharge medical record review																		Х

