4.2 Observational (non-treated) cohort

The medical record of each infant enrolled in the observational cohort will be reviewed regularly until hospital discharge to collect pre-specified clinical data. Each infant in the observational cohort will also undergo respiratory mechanics measurements on study days 1, 7 and \leq 48 hours after completing the 14-day study period (see section 4.3.3). A tracheal aspirate for culture will also be collected \leq 48 hours after completing the 14-day study period (see section 4.3.2). Oxygen saturation data (SpO₂) will be recorded using continuous pulse oximetry. To collect this data, a research pulse oximeter will be placed in addition to the pulse oximeter used for clinical monitoring. This second device will enable reliable data collection, storage, and analysis. Nursing and medical staff will be instructed to use the clinical oximeter for all clinical monitoring.

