5.1.1.2 Phase 1 Trial

The medical record will be reviewed as follows throughout the phase 1 trial:

• Daily review of the medical record and discussion with the medical team, nursing, and respiratory staff to assess for adverse events

- Daily review of weight, vital signs (heart rate, blood pressure, oxygen saturation), and fluid balance (including urine output) recorded by nursing staff in the electronic medical record (EPIC) flow sheet
- Daily respiratory support data (mode of ventilation, settings, FiO₂, and calculated respiratory severity score: mean airway pressure x FiO₂) recorded in EPIC
- Daily review of administered medications (name, dose, route, and interval)
- Daily review of any clinically ordered laboratory tests and radiographic imaging.

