5.1.1.3 Observational (non-treated) cohort

The medical records of infants who are enrolled in the observational cohort will be reviewed daily for 14 days beginning after enrollment. Respiratory support data (mode of ventilation, settings, FiO₂, and calculated respiratory severity score: mean airway pressure x FiO₂) will be abstracted from EPIC.

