8 SAFETY MANAGEMENT

8.1 Clinical Adverse Events

Clinical adverse events (AEs) will be monitored throughout the study. These will constitute both the defined tolerability drug endpoints and additional events that are observed clinically or by diagnostic testing (imaging, laboratory analyses) throughout the trial and pose a risk to the study participant.

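### Table 7 compares tube obstruction and unplanned extubation between the cohorts, but active daily ascertainment of these events is specified only for trial infants

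*Combined protocol and SAP*

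**What the plan says.** **The comparison.** In Table 7 (section 6.3.3), the row for secondary safety endpoints plans: "Data on the rates of endotracheal tube obstruction, unplanned tracheal extubation, and audiology testing results will be compared between the trial and observational cohorts". For the observational cohort it describes the availability of these endpoints as "Yes, for some endpoints". It names no data source for the two tube events.

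**Trial infants.** Section 5.1.1.2 requires: "Daily review of the medical record and discussion with the medical team, nursing, and respiratory staff to assess for adverse events". Section 8.1 describes the clinical adverse events to be monitored: "These will constitute both the defined tolerability drug endpoints and additional events that are observed clinically or by diagnostic testing". The trial block of Table 1 has a daily adverse event assessment row from day 0 to day 15. Section 4.7 also makes a count of tube obstructions and unplanned extubations necessary, because two such events combined bar an infant from resuming the drug trial.

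**Observational infants.** Section 5.1.1.3 says: "The medical records of infants who are enrolled in the observational cohort will be reviewed daily for 14 days beginning after enrollment". It then itemises the content: "Respiratory support data (mode of ventilation, settings, FiO₂, and calculated respiratory severity score: mean airway pressure x FiO₂) will be abstracted from EPIC". Section 4.2 adds that records are "reviewed regularly until hospital discharge to collect pre-specified clinical data", without a list. The observational block of Table 1 covers tracheal aspirate, oximetry, respiratory support, pulmonary mechanics, audiology and discharge record review. It has no row for adverse events or tube events.

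**The concern.** Comparing event rates between two groups requires that events be looked for in the same way in both. Here one group has a daily active search that includes talking to the staff who handle the tube. The other has a chart abstraction whose listed fields do not include the events. If some control events go unrecorded, the treated rate looks higher than the control rate even when the drug does nothing.

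The observational cohort is the trial's only concurrent source of background rates for tube events, and section 9.4.3 expects the data to inform later phase 2 and 3 trials. An artefactual excess of tube events could be carried forward as a tolerability signal.

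**Working it through.** The documents give no expected rate, power or test for tube obstruction or unplanned extubation, so there is no stated figure to reproduce. The check is a side-by-side reading, followed by an illustration under stated assumptions.

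**1. What is specified for each cohort during the 14 days**

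| Item | Trial infants | Observational infants |
|---|---|---|
| Daily record review | Yes (5.1.1.2) | Yes (5.1.1.3) |
| Discussion with bedside staff | Yes (5.1.1.2) | Not specified |
| Daily adverse event row in Table 1 | Yes | No |
| Running count of tube events needed | Yes (4.7) | No |
| Extubation noticed | Yes (4.7) | Usually: mode abstracted daily (5.1.1.3), aspirate brought forward to extubation (4.4), mechanics stopped if ventilation is not resumed within 48 hours (4.7) |
| Planned or unplanned extubation | Through adverse event monitoring | Not a listed item |
| Extubation with quick re-intubation | Through adverse event monitoring | Not a listed item |
| Tube replaced for obstruction | Through adverse event monitoring | Not a listed item |

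Obstruction is the more exposed of the two endpoints. A tube exchange need not change ventilation mode, settings, FiO₂ or the severity score, which are the fields section 5.1.1.3 names.

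Audiology, the third item in the Table 7 comparison, is not affected: its results are reviewed in both blocks of Table 1.

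**2. Effect of unequal capture on the rate ratio**

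Let the true rate be r in both cohorts (no drug effect), with a share c_T of events captured in treated infants and c_O in observational infants.

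Apparent rate ratio = (r × c_T) / (r × c_O) = c_T / c_O.

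Set c_T = 1. The values of c_O are assumptions; the documents give none.

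- c_O = 0.90: 1 / 0.90 = 1.11
- c_O = 0.75: 1 / 0.75 = 1.33
- c_O = 0.50: 1 / 0.50 = 2.0

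The ratio does not depend on r. The absolute difference does. At an assumed risk of 20% it is 20% − 18% = 2 points, 20% − 15% = 5 points and 20% − 10% = 10 points respectively.

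**3. Effect on a significance test**

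Section 6.4 gives up to 24 evaluable trial infants and 12 to 28 observational infants. Table 7 names no test for these rates, so a two-sided Fisher exact test at p ≤ 0.05 is assumed. The table shows the chance of a significant result with equal true risks and full capture in treated infants.

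| Groups | Assumed risk | c_O = 1 | c_O = 0.75 | c_O = 0.50 |
|---|---|---|---|---|
| 24 vs 28 | 10% | 2.2% | 3.3% | 6.1% |
| 24 vs 28 | 20% | 3.3% | 5.1% | 12.8% |
| 24 vs 28 | 30% | 3.7% | 7.5% | 20.7% |
| 24 vs 12 | 10% | 1.6% | 0.8% | 0.3% |
| 24 vs 12 | 20% | 2.5% | 2.1% | 2.8% |
| 24 vs 12 | 30% | 2.7% | 3.9% | 8.8% |

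False significance is limited except with poor capture, a high event risk and the larger control group. The main harm is a biased estimate.

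**The case against.** The strongest reply is that the control data probably exist. Table 7 says values are available for some observational endpoints, and the same row names these two for comparison. Section 4.2 provides for further clinical data, the synopsis has clinical data collected daily from the record, and section 9.2 makes the hospital record the source for every subject. The case report forms are not shown. Both events are overt, the infants are in the same intensive care unit, and several procedures depend on staff knowing about an extubation. The trial-side wording is also general: section 5.1.1.2 does not name tube events either.

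Much of this stands. A reader might infer that there are no control data at all. The documents do not support that: they show a gap in what is specified and do not show that data are missing. A reader might also cite the restriction of weekly serious adverse event review to trial infants (section 5.1.1.4). That covers follow-up after the 14 days and says little about events during them.

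What remains is narrower. Where the plan does itemise observational data, the two events are absent. Knowing that ventilation stopped does not show why, and a tube exchange may leave no trace in the listed fields. Nothing says that both cohorts use the same source and definition.

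**Conclusion.** The concern holds as a specification gap of moderate weight. As written, the two cohorts are not ascertained alike for the tube events that Table 7 compares, and the likely direction of error is against tobramycin. The size cannot be known from the documents. The apparent ratios of 1.11 to 2.0 rest wholly on assumed control capture of 90% to 50% with full capture in treated infants. If capture is equal, there is no bias from this source.

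Three stronger readings should be resisted:

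- **A drug effect inflated by a known factor.** No capture rate is given, so no single ratio can be claimed.
- **The main local safety concern.** These are two of six exploratory secondary safety endpoints (section 5.2.2), and the inhalational reactions named in section 1.6.2.3 are others, such as cough and bronchospasm.
- **A threat to dose finding.** Neither event is a named component of the primary composite (section 5.2.1), and this cohort comparison plays no part in the study stopping rules (section 5.2.5).

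Equal ascertainment would not make the comparison causal. Families choose the cohort (section 9.6), so it remains non-randomised and descriptive.

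**What to change.** 1. Add tube obstruction requiring replacement, and unplanned extubation, to the daily abstraction in section 5.1.1.3 and to the observational block of Table 1.
2. State in Table 7 that, for the comparison, events in both cohorts are counted from the medical record, with the same definition, over the 14-day period.
3. Report the rates per intubated day. Trial infants can leave early (section 4.7) while observational data collection runs for 14 days, so counts per infant would rest on unequal time at risk.
4. Report events in trial infants that are learned of only through staff discussion descriptively, outside the comparison.

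The cost is two extra fields in a chart review that already takes place daily, plus the loss from the formal comparison of any trial event that never reached the record. No change to treatment or clinical management is involved.
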